EEA	European Economic Area
EU	European Union
GP	General Practitioner
ICD	International classification of diseases
ILI	Influenza-like illness
I-MOVE	Influenza – Monitoring Vaccine Effectiveness in Europe
IQR	Interquartile range
IVE	Influenza vaccine effectiveness
OR	Odds ratio
RT-PCR	Reverse-transcriptase polymerase chain reaction
SARS-CoV-2	Severe acute respiratory syndrome coronavirus 2
VC	Vaccination coverage
VE	Vaccine effectiveness

➤ *Arrow marks indicate the sections that countries/study sites should adapt and provide details for in their study annexes.*

Executive summary

The end of 2019 saw the emergence of a novel severe acute respiratory syndrome coronavirus 2 (SARS-CoV-2) causing coronavirus disease 2019 (COVID-19). As of August 2023, eight vaccines had been authorised by the European Commission based on the scientific opinion of the European Medicines Agency (EMA) for use in the European Union (EU): Bimervax (previously COVID-19 Vaccine HIPRA), Comirnaty, COVID-19 Vaccine Valneva, Jcovden (previously COVID-19 Vaccine Janssen), Nuvaxovid (previously Novavax), Spikevax (previously COVID-19 Vaccine Moderna), Vaxzevria (previously COVID-19 Vaccine AstraZeneca), and VidPrevtyl Beta (indicated as a booster). In addition, four adapted vaccines have also been authorised: Comirnaty Original/Omicron BA.1, Comirnaty Original/Omicron BA.4-5, Spikevax bivalent Original/Omicron BA.1, and Spikevax bivalent Original/Omicron BA.4-5. Many other vaccines are under rolling review [4].

Influenza viruses undergo frequent genetic and antigenic changes. The influenza vaccine is reformulated each year and annual re-vaccination is recommended. Observed influenza vaccine effectiveness (IVE) varies from year to year between population sub-groups (age groups, risk groups) and differs for the various influenza types, subtypes and genetic clades, and outcomes measured. Immunological correlates of protection are not well defined. In 2017, the European Medicines Agency (EMA) formally adopted new guidelines on influenza vaccines covering, inter alia, post-authorisation studies of vaccine effectiveness, including brand-specific IVE data [5].

There is variation among the available influenza vaccine products currently in use for EU/EEA immunisation programmes, the target groups for vaccination, and the vaccination coverage across countries [6]. New vaccines are being developed for which limited or no effectiveness data are yet available in the EU. A comparison by vaccine type (adjuvanted vs nonadjuvanted, live attenuated vs inactivated, egg- vs cell-based), group (split virion, subunit, etc.) and product could provide essential information for vaccine recommendations and health economic assessments.

In 2020, the European Commission stressed the importance of continuously monitoring the safety and effectiveness of vaccines in the EU/EEA in the post-authorisation phase, with particular emphasis on COVID-19 vaccines in the context of the ongoing pandemic [7]. The 2018 'Council Recommendation on Strengthened Cooperation against Vaccine-preventable Diseases' already called on ECDC and EMA to cooperate to ensure the continued monitoring of vaccines and vaccination in use in EU/EEA vaccination programmes [8]. This request was subsequently formalised as part of the extended EMA regulatory mandate [9] and ECDC's newly amended mandate [10], requiring the two agencies to develop a structured and independent post-authorisation vaccine monitoring platform, initially prioritising COVID-19 vaccines. ECDC and EMA officially established and launched the platform in May 2022, with the intention of bringing together public health and regulatory experts to discuss the studies needed to generate real-life evidence on the safety and effectiveness of vaccines in use in EU/EEA immunisation programmes.

From 2020, ECDC began building infrastructure to perform COVID-19 vaccine effectiveness (CVE) studies using the lessons learned from other vaccine effectiveness studies. One such study was the ECDC-funded project I-MOVE (Influenza – Monitoring Vaccine Effectiveness in Europe), under which IVE was measured in Europe using primary care sentinel surveillance systems since the 2007–2008 influenza season [11, 12]. The infrastructure will be used to build a system that regularly monitors vaccine effectiveness and performs studies, including impact and burden of disease studies, in different settings. Depending on the setting, information will be provided on different outcomes (severe disease, moderate disease, transmission, etc). The overall project is called VEBIS (Vaccine Effectiveness, Burden and Impact Studies) and it includes different networks of study sites/countries/infrastructures, where the multi-country studies are conducted.

This document presents the core protocol for ECDC studies of CVE and IVE against symptomatic laboratory-confirmed influenza or SARS-CoV-2 infection, respectively, at primary care level. This core protocol presents the main elements for a multicentre (multi-country) study of IVE/CVE at primary care level, outlining the agreed methods for collecting data related to influenza and SARS-CoV-2 at country level, and includes a plan for the pooled analysis. The combination of data from multiple study sites will allow for studies with more statistical power to meet more specific objectives. The protocol can be implemented for COVID-19 and/or influenza.

The proposed method is a case-control study using a test negative design. The study population consists of people of all ages, belonging to the target group for COVID-19 or influenza vaccination, presenting to primary care with symptoms of acute respiratory infection (ARI) or influenza-like illness (ILI), and no contraindication for being vaccinated with the vaccine of interest.

This protocol is adapted from the I-MOVE and I-MOVE+ generic protocols [1, 2] and the I-MOVE-COVID-19 generic protocol [3] and is written in a generic manner. The specificities of each study site's influenza and/or COVID-19 VE study can be detailed in the individual site protocol annexes (Annex 5).

This core protocol is primarily intended to guide the implementation of ECDC-funded studies. However, ECDC encourages the conduct of vaccine effectiveness studies, using this protocol as a basis, in countries not currently planning to participate in ECDC-funded studies. The use of consistent protocols will facilitate the comparability of study results across studies, countries, and study sites.

This document presents version 1.0 of the core protocol which is an evolving document. This document will be updated and revised as necessary.

Protocols for IVE and/or CVE studies in other settings, such as in hospitals or in long-term care facilities, are also available on [ECDC's website](#).

1 Background

1.1 Context: COVID-19

The end of 2019 saw the emergence of a novel severe acute respiratory syndrome SARS-CoV-2, which can cause coronavirus disease 2019 (COVID-19).

As of August 2023, eight authorised COVID-19 vaccines and four adapted vaccines have received conditional marketing authorisation by the European Commission (EC) based on the scientific opinion of the European Medicine Agency (EMA) [4], as shown in Table 1 below.

Table 1. COVID-19 vaccines authorised and in use in the EU/EEA as of August 2023

Vaccine	Age of recommendation	Primary dose regimen	Booster dose
Bimervax (previously COVID-19 Vaccine HIPRA)	16 years +	No	May be given as a booster at least six months after a previous mRNA COVID-19 vaccine.
Comirnaty	Six months +	Single dose may be given in individuals aged five years + for primary vaccination regardless of prior COVID-19 vaccination status. In children aged from six months to four years, two doses are given three weeks apart, followed by a third dose given at least eight weeks after the second dose. Different doses are available for adults and adolescents (aged 12 years +), children aged five to 11 years, and children aged six months to four years.	May be given as a booster at least three months after the most recent dose in individuals aged six months +. Different doses are available for adults and adolescents (aged 12 years +), children aged five to 11 years, and children aged six months to four years.
Comirnaty Original/Omicron BA.1	12 years +	No	May be given as a booster at least 3 months after the most recent dose in individuals aged 12 years +.
Comirnaty Original/Omicron BA.4-5	Six months +	Single dose may be given in individuals aged five years + for primary vaccination regardless of prior COVID-19 vaccination status. In children aged from six months to four years, two doses are given three weeks apart, followed by a third dose given at least eight weeks after the second dose. Different doses are available for adults and adolescents (aged 12 years +), children aged five to 11 years, and children aged six months to four years.	May be given as a booster at least three months after the most recent dose in individuals aged six months +. Different doses are available for adults and adolescents (aged 12 years +), children aged five to 11 years, and children aged six months to four years.
COVID-19 vaccine Valneva (inactivated, adjuvanted)	18 to 50 years	Two doses, given four weeks apart.	No
Jcovden	18 years +	Single dose.	May be used as a booster dose given at least two months after the first dose of Jcovden. A booster dose may also be given after primary vaccination with an mRNA or adenoviral vector vaccine, with the timing according to the official recommendations issued at national level by public health bodies.

Vaccine	Age of recommendation	Primary dose regimen	Booster dose
Nuvaxovid	12 years +	Two doses, given three weeks apart.	
May be used as a booster dose for individuals aged 18 years + around six months after primary vaccination with Nuvaxovid.
 
A booster dose of Nuvaxovid may also be given after primary vaccination with an mRNA vaccine or adenoviral vector vaccine, according to the official recommendations issued at national level by public health bodies.

Spikevax	Six months +	
Two doses, given 28 days apart.
 
Different doses are available for adults and adolescents (aged 12 years +), children aged six to 11 years, and children aged six months to five years.
 
An additional dose of Spikevax may be given to people aged six years + with a severely weakened immune system, at least 28 days after their second dose.
	
May be given as a booster in individuals aged six years + at least three months after the second dose of Spikevax, or another mRNA vaccine or an adenoviral vector vaccine.
 
Different doses are available for adults and adolescents (aged 12 years +), and children aged six to 11 years.

Spikevax bivalent Original/Omicron BA.1	Six years +	No	
May be given to individuals aged six years + at least three months after primary vaccination or a booster dose with a COVID-19 vaccine.
 
Different doses are available for adults and adolescents (aged 12 years +), and children aged six to 11 years.

Spikevax bivalent Original/Omicron BA.4-5	Six years +	No	
May be given to individuals aged six years + at least three months after primary vaccination or a booster dose with a COVID-19 vaccine.
 
Different doses are available for adults and adolescents (aged 12 years +), and children aged six to 11 years.

Vaxzevria	18 years +	Two doses, with second dose given between four and 12 weeks after the first dose.	
A booster dose may be given at least three months after the second dose of Vaxzevria.
 
A booster dose of Vaxzevria can also be given to adults who have had two doses of an authorised mRNA COVID-19 vaccine according to the official recommendations issued at national level by public health bodies.

VidPrevtyn Beta	18 years +	No	May be used as a booster dose at least four months after a previous mRNA or adenoviral vector COVID-19 vaccine.

By January 2021, all 30 EU/EEA countries had launched COVID-19 vaccination campaigns, and different COVID-19 vaccines have been gradually introduced as they have become available through the EU Vaccines Strategy [13]. Beside healthcare workers and residents in long-term care facilities, the vaccination strategy in the general population had an age-based staggered approach prioritising elderly people. Most of the vaccines used to date including booster vaccines were mRNA vaccines [14].

Post-marketing CVE studies are important to determine whether vaccines are effective or not among the target group for vaccination in real life conditions and over time. Under real life conditions, CVE studies can include incomplete schedules, mixed vaccine products and varying proportions of SARS-CoV-2 variants circulating. Settings

of CVE studies can be varied and include study populations of COVID-19 patients admitted to hospital, healthcare worker populations, residents, and workers of long-term care facilities, as well as outpatient settings [15-18]. Each setting provides a particular piece of information on the effectiveness of COVID-19 vaccines.

CVE studies among people presenting at primary care/outpatient level generally provide information on how well the COVID-19 vaccines perform against less severe disease. This information complements that of CVE against severe outcomes and is an important factor for public health decision making around vaccine policy. Long-term monitoring of CVE and impact in a variety of settings is crucial to understand the value of the vaccines as a public health intervention and provides important information for future vaccine composition.

1.2 Context: influenza

In 2009, the Council of Ministers recommended that all EU Member States reach an influenza vaccination coverage of 75% in key target groups (such as older people, healthcare workers and individuals at risk of more severe disease) [19]. A survey performed by ECDC, reviewing coverage in the three seasons between 2018 and 2021, concluded that although in the 2020–21 season there was generally increased uptake, the recommended target was not reached in most countries [6]. In the same survey, it was also documented that during 2021–22 season, several EU/EEA countries expanded their influenza vaccine recommendations to additional age groups compared to previous seasons especially in children/adolescents and some lowered the lower age limit in elderly adults as compared to 2017/18.

Influenza viruses undergo frequent genetic and antigenic changes. As a consequence, the influenza vaccine is reformulated each year and annual revaccination is recommended. The available vaccine products, the target groups for vaccination and vaccination coverage all vary across countries. The available influenza vaccines are wide-ranging and can be trivalent or quadrivalent, adjuvanted or non-adjuvanted, live attenuated or inactivated, egg-based or cell-based, split virion or subunit vaccines etc. Due to this variation, IVE comparisons by vaccine type (adjuvanted vs non-adjuvanted, live attenuated vs inactivated, egg- vs cell-based), group (split virion, subunit, etc.) and product (vaccine brands) would provide essential information for vaccine recommendations and health economic assessments.

Observed IVE varies from year to year, between population subgroups (e.g. age and risk groups) and varies according to the measured outcome (laboratory confirmed influenza virus by (sub)type/clade or clinical outcome). IVE may vary between vaccine types and products, by time since vaccination and according to previous influenza infection and influenza vaccine history.

Conducting annual IVE estimates at the European level right at the beginning of a seasonal influenza epidemic/pandemic may provide critical and additional evidence for public health recommendations. For example, the recommended target groups for the current season's vaccine can be expanded/amended if circulating strains are causing severe illness but there are good/high early IVE estimates. Alternatively, very low early IVE estimates could prompt recommendations to use other non-pharmaceutical interventions (such as use of face masks or social distancing) in specific settings, or antivirals as a preventative measure. Lacking early season IVE results could also result in a failure to use alternative measures, leading to increased disease burden and increased costs.

Monitoring the IVE along the course of the epidemic/pandemic allows more precise estimates of the impact of current vaccination strategies on the burden of disease to support vaccination campaigns, and may trigger further investigations on seasonal and pandemic vaccines (improve composition, use of adjuvants, different doses, need for booster doses). Additionally, IVE studies can counterbalance the reports of adverse events following immunisation by providing elements for adequate risk management and cost-effectiveness analysis.

Early-season IVE by product and influenza type/subtype is also critical for the World Health Organization (WHO) vaccine composition meeting discussions, in which the vaccine selections for the subsequent season are decided.

Furthermore, new vaccines are being developed for which limited or no effectiveness data are yet available in the EU. In case of an influenza pandemic, an established EU platform to rapidly measure IVE by vaccine type and product will allow the evaluation of any pandemic vaccine and the adaptation of preventive and control strategies.

Besides measuring IVE by influenza (sub)type early and late in the season and by vaccine type, these IVE studies can be used to help answer further research questions, such as the effect of previous influenza vaccination on current season influenza infection, to what extent IVE may decline within the season, the effect of first influenza infection on subsequent IVE and the measurement of IVE against different influenza clades or genetic variants.

Currently, observational studies are the most frequently used method to provide estimates of IVE in Europe. Long-term multicentre studies may provide adequate sample size and data quality to answer some of these questions.

1.3 Context: integrated respiratory surveillance

Across Europe, it is recommended that surveillance for respiratory pathogens (including both influenza and SARS-CoV-2) should be integrated [20-22]. Effective integrated respiratory surveillance systems should provide data sufficient for monitoring the spread and intensity of respiratory viruses to guide control measures and mitigate their impact. These systems will also be important in the event of future pandemics. In this context, well-designed, representative sentinel surveillance systems in primary and secondary care should remain the central surveillance method for acute respiratory infections. Sentinel systems provide robust epidemiological data that are routinely collected using common syndromic case definitions with reliable denominators and integral microbiological testing that can be extended to multiple viruses. This makes them ideal as the basis of integrated impact assessment of influenza, COVID-19, and potentially other respiratory virus infections. Monitoring systems should be sensitive enough to detect virus variants, accurately follow virus-specific disease incidence by level of severity/age/place, and assess vaccine effectiveness.

Further information on integrated respiratory surveillance can be found in the [Operational considerations for respiratory virus surveillance in Europe \(18 July 2022\)](#).

1.4 ECDC COVID-19 and influenza vaccine effectiveness studies

In 2018, the Council recommendation on Strengthened Cooperation against Vaccine-preventable Diseases (2018/C 466/01) called on the European Commission to work with the Member States and with the support of the European Medicines Agency (EMA) and in cooperation with ECDC to 'continuously monitor the benefits and risks of vaccines and vaccinations at EU level including through post-marketing authorisation studies'. In 2020, the European Commission stressed the importance of continuously monitoring the safety and effectiveness of vaccines in the EU/EEA in the post-authorisation phase, with particular emphasis on COVID-19 vaccines in the context of the ongoing pandemic [7]. This was subsequently formalised as part of the extended EMA regulatory mandate [9] and ECDC's newly amended mandate [10], which request the two Agencies to develop a structured and independent post-authorisation vaccine monitoring platform, initially prioritising COVID-19 vaccines. ECDC and EMA officially established and launched a platform in May 2022, with the intention of bringing together public health and regulatory experts to discuss the studies needed to generate real-life evidence on the safety and effectiveness of vaccines in use in EU/EEA immunisation programmes.

Already in 2020, utilising the lessons learned from other vaccine effectiveness studies, ECDC started building infrastructure to perform COVID-19 vaccine effectiveness (CVE) studies (Table 2). The purpose of this infrastructure is to build a system to regularly monitor VE and perform studies in different settings, and depending on the setting, to provide information on different outcomes (severe disease, moderate disease, infection, transmission, etc). The multi-country approach is also one of the key features that characterises the studies, with a foreseen approach of progressive inclusion of more countries over time.

Table 2. Settings and types of study performed within the ECDC VEBIS infrastructure as of July 2023

Setting	Type of study	Main outcome	Pathogens included	Protocol/s
Hospitals	Test negative design	Severe disease (~SARI)	Influenza and COVID-19	[23]
Healthcare workers cohort	Prospective cohort study	Infection	COVID-19 (pilot: Influenza)	[24, 25]
Electronic healthcare databases	Retrospective cohort study	Hospitalisation, death	COVID-19	[26]
Primary care	Test negative design	Moderate disease (~ARI/ILI)	Influenza and COVID-19	This document

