2.2 Secondary objectives

The secondary objectives are to measure overall and product-specific IVE and CVE against symptomatic laboratory-confirmed influenza or SARS-CoV-2 infection, by:

- risk groups (such as clinically vulnerable people, pregnant women, etc.);
- sex;
- age groups;
- specific vaccination target groups;
- calendar time;
- time since vaccination;
- vaccine schedules;
- delay between doses (if more than one dose received);
- combination of vaccine products (if applicable).

Secondary objectives include also identifying key phenotypic or genotypic evolutions that could affect vaccine performance and to estimate IVE and CVE against specific influenza (sub)clades or SARS-CoV-2 genetic variants.

- *Each study site/country to specify primary objectives of their study as measuring CVE and IVE or CVE only or IVE only.*
- *Each study site/country to specify the (additional) secondary objectives of their study.*

¹ Countries only participating in CVE can ignore references to measurement of IVE throughout the document and vice versa.

3 Methods

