3.13.3 Pooled analysis

The higher sample size for the pooled analysis will provide more precision around the VE estimates. Data can be coded as outlined in Annex 1, or a data dictionary can be provided by the study teams that includes the variable names, descriptions and coding. The central hub (performing the pooled analysis) will perform data cleaning and document and share any further data cleaning and analysis with all study coordinators to ensure it can be reproduced.

See Annex 4 for detailed guidelines for analysis, including the pooled analysis. For the pooled data, interim analyses will be conducted in different periods if appropriate and according to the available sample size.

The timing to conduct each interim analysis will depend on the time needed to reach the appropriate sample size. This will depend mainly on the incidence of influenza (for IVE) or COVID-19 (for CVE), vaccination coverage, the recruitment strategy and the number of participating primary care practices.

The pooled analysis will be carried out in a similar way to the study site-specific analysis. Country or study site will be included as a fixed effect or potentially as a random effect in a multilevel model. Statistical heterogeneity between study sites will be determined, using the Q-test and the I^2 index.

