5.1.8 Other potential biases

Controls could come from different source populations with varying risk for infection with influenza or SARS-CoV-2, varying probability for acquiring influenza or COVID-19 vaccination, etc. (e.g. depending on time of year). Time (onset date) will be used to adjust for seasonal differences. Analyses will also be stratified by time (e.g. onset quarter). For COVID-19, the success of vaccination programs in some countries has resulted in only a small proportion of population remaining unvaccinated. This population may be different from the general population. Rather than using unvaccinated as the reference group in CVE, analyses using relative VE (e.g. booster vaccination compared to primary course vaccination) could be considered, although a simulation study is recommended to understand the implications of this analysis in a multicentre context.

- *Each country to describe timeline of vaccination and vaccine coverage for different target groups.*

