This study is a case control study (test-negative design). The measure of association is an odds ratio (OR). This can be measured by logistic regression. An OR = 1 indicates no association between an exposure and the outcome. An OR > 1 indicates a potential risk factor, an OR < 1 indicates a potential protective factor, noting that the confidence interval around the OR helps with its interpretation.

For vaccination as preventive factor, the VE can be computed as $VE = (1 - OR) * 100$. A 95% confidence interval is computed around the point estimate.

Pooled crude VE estimates

We will estimate crude VE, adjusting for study site as a fixed effect and adjusting for symptom onset time. We will adjust for study site, as this is part of the multicentre study design, and for calendar time, as this is an integral part of the test-negative design.

The primary analysis for the pooled VE estimates will be a one-stage approach, where individual data from study sites are pooled and study site is included as a fixed effect covariate in the model. The one-stage analysis is useful approach, particularly if smaller study sites are included and it can provide good modelling flexibility. Study site can be included as a fixed effect or if enough study sites are available potentially as a random effect in a multilevel model. The fixed effect assumes the same VE for all study sites, with differences due to random variation, rather than to essential differences in VE.

Statistical heterogeneity between study sites will be determined, using Q-test and the I2 index [28] and a two-stage pooled analysis approach can be carried out in a sensitivity analysis.

Pooled stratified analysis

The analysis can be stratified according to (if sample size allows):

- age groups (e.g. <20, 20-44, 45-64, 65+ years);
- sex;
- presence of at least one chronic condition, or specific chronic conditions; and
- calendar time and time since vaccination.

A sufficient sample size should be planned in order to ensure enough people in each stratum for a precise estimate. Effect modification should be assessed comparing the VE across the strata of the baseline characteristics. Confounding should be assessed by comparing crude and adjusted VE for each baseline characteristic.

Pooled multivariable analysis

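### If vaccine effectiveness differs between sites that join early and sites that join late, a change in the contributing sites can appear as a change in pooled effectiveness by calendar time

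*Protocol*

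**What the plan says.** **The set of sites may change.** Section 1.4 foresees building the multi-country studies "with a foreseen approach of progressive inclusion of more countries over time". This is background on the whole infrastructure, of which Table 2 lists this primary care study as one part. Separately, section 3.3 starts inclusion for influenza from each country's own first positive case.

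**VE over time is an intended result.** Section 2.2 begins "The secondary objectives are to measure overall and product-specific IVE and CVE against symptomatic laboratory-confirmed influenza or SARS-CoV-2 infection, by" and its list includes "calendar time". Section 5.1.8 plans time strata: "Analyses will also be stratified by time (e.g. onset quarter". In Annex 4, the pooled stratified analysis may use "calendar time and time since vaccination" if sample size allows. Section 3.13.3 adds: "For the pooled data, interim analyses will be conducted in different periods if appropriate and according to the available sample size".

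**The strata invite comparison.** Directly after the list containing calendar time, Annex 4 says "Effect modification should be assessed comparing the VE across the strata of the baseline characteristics".

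**The model has one VE.** The primary pooled analysis is one-stage, with study site as a fixed-effect covariate. Annex 4 says of this: "The fixed effect assumes the same VE for all study sites, with differences due to random variation". A random site effect is mentioned as a possibility. Heterogeneity is examined by the Q-test, I², forest plots and a qualitative decision on excluding sites. A two-stage random-effects analysis is optional.

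**The concern.** A site covariate lets each site have its own odds of being a case among the unvaccinated. It does not let each site have its own VE. In each period the model therefore returns roughly an information-weighted average of the VEs of the sites that contributed in that period. When the sites change, the weights change, and so may the average.

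The protocol gives reasons to expect VE to vary. Products, target groups and vaccination coverage differ between countries (section 1.2). IVE may vary by product and by infection and vaccination history (same section). The optional two-stage model explicitly allows site estimates to differ.

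The infrastructure is meant for regular monitoring of VE. A fall produced by the mix of sites could be read as waning or as the effect of a new variant, and a rise as an improvement. The issue is bias in the comparison of periods, not the width of any one interval.

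**Working it through.** **Is there a figure of the plan's own to reproduce?** Not on this point. As a check that the log odds ratio variance used here matches the protocol's, take the Table 4 row with OR 0.5, coverage 0.5 and precision 0.2. With p0 = 0.5, p1 = 0.5×0.5/(0.5 + 0.5×0.5) = 0.333 and SE = ln(0.7/0.5)/1.96, n = [1/(p0(1−p0)) + 1/(p1(1−p1))]/SE² = 288.4, so 289. Table 4 states 289.

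**Inputs (all assumed; the protocol gives none of them).** Each site contributes 500 controls per period, with 50% coverage and case:control odds of 0.6 among the unvaccinated. Four original sites contribute in period 1, two new sites are added in period 2, and two more in period 3 (eight in all). VE is constant over time at every site. The model is logistic with site intercepts and one vaccination effect, fitted to expected counts.

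**Worked case, original VE 50%, new VE 30%.**

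- Original site: 75 vaccinated and 150 unvaccinated cases, 250 vaccinated and 250 unvaccinated controls. Variance of log OR = 1/75 + 1/150 + 1/250 + 1/250 = 0.0280, weight 35.7.
- New site: 105 vaccinated cases, the rest as above. Variance = 1/105 + 1/150 + 1/250 + 1/250 = 0.0242, weight 41.3.
- Inverse-variance average in period 3: [4×35.7×ln 0.5 + 4×41.3×ln 0.7]/[4×35.7 + 4×41.3] = −0.513, so VE is about 40.1%. The one-stage logistic fit gives −0.514, VE 40.2%.
- Period 1 against period 3: the log OR changes by 0.179. SE = √(0.0837² + 0.0568²) = 0.101, z = 1.77. A two-sided 5% test would reject in about 42% of studies.

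| Original / new VE (assumed) | Pooled VE, period 1 → 3 | False shift | z | Rejection |
|---|---|---|---|---|
| 50 / 50 | 50.0 → 50.0 | 0 | 0 | 5% (nominal) |
| 50 / 40 | 50.0 → 45.1 | 4.9 | 0.93 | 15% |
| 50 / 30 | 50.0 → 40.2 (43.5 in period 2) | 9.8 | 1.77 | 42% |
| 60 / 30 | 60.0 → 45.5 | 14.5 | 2.93 | 83% |

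**Second layout.** With 300 cases and 300 controls per site per period, four sites and then eight, and coverage of 30% or 50%, the shift is about 4 to 16 points for VE differences of 10 to 30 points. It can go either way: original 40% and new 60% gives 40.0 → 50.7 at 50% coverage. With equal VE the shift is zero, also when new sites have different coverage.

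**Same model, constant set of sites.** Restricted to the four original sites, pooled VE does not move in any scenario.

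**Would the planned Q-test notice?** With eight sites (7 df) in the last period alone, Q rejects in about 54% (50/30), 16% (50/40) and 96% (60/30) of studies. With all three periods combined the figures are about 89%, 32% and 100%.

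**The case against.** Several points on the other side stand.

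- A reader might infer that any change in the sites shows up as a change in VE. It does not. VE must differ systematically between early and late sites. Differences in incidence or coverage alone are absorbed by the site term, and random site differences produce no shift in a given direction on average.
- A reader might also infer that the protocol schedules new sites between compared periods. Section 1.4 gives no entry rule or dates, and countries might join only between seasons. That would protect comparisons within a season but not between seasons.
- The Annex 4 sentence on comparing strata speaks of baseline characteristics, which calendar time strictly is not. No test between periods is prescribed, so the rejection percentages describe a test that a reader of the results might apply, not a planned one.
- Safeguards exist: site-specific VE is part of the primary objective, country forest plots are drawn, site characteristics are reviewed, and different sites may be excluded. In the scenarios above the Q-test signals at least as often as the false trend reaches significance. Annex 4 also tests interactions, though it does not name site by vaccination.

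These safeguards do not close the gap. They address differences between sites, and nothing directs them at a comparison of periods. Section 5.1.1 concedes that the heterogeneity test has low power with few sites. The optional two-stage model still averages whichever sites are present. Nor is this merely a detail left to a later plan: Annex 4 is the detailed pooled analysis plan and it fixes this model.

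**Conclusion.** The point holds conditionally. With progressive entry of countries and a pooled model that has site intercepts and one common VE, a change in the contributing sites can look like a change in pooled VE over calendar time when early and late sites differ in VE. The illustrative size is about 5 to 14.5 points for assumed differences of 10 to 30 points, and zero when VE is equal. These figures rest on assumed site VEs and site sizes, and on all new sites differing in the same direction. The documents do not support saying that a false trend will occur, or how large it would be. They do show that nothing in section 3.13 or Annex 4 would separate such a trend from a true one.

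**What to change.** In Annex 4, under the pooled stratified analysis, add that whenever pooled VE is compared across calendar periods or seasons:

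1. the contributing sites, with their case and control numbers, are reported for each period;
2. a sensitivity analysis is restricted to sites that contributed in all compared periods or, where cell sizes allow, a model with site-by-vaccination terms is fitted so that change is estimated within sites;
3. a difference between periods is interpreted as a change in VE only if that result agrees.

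The all-sites estimate should remain the estimate of current VE. Making a fixed panel the sole basis for every statement about change would go too far. It would drop sites with no cases in one period, which staggered epidemics make likely, and would narrow the population represented.

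The cost is one table and one further model on data already pooled. The downside is wider intervals for the trend and a narrower set of sites behind it. Site-by-vaccination terms may be unusable where cells fall below the minimum sizes that Annex 4 itself sets.
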